### 7.2.1.2. Summaries of Laboratory Abnormalities

A summary (number and percentage of subjects) for treatment-emergent laboratory abnormalities will be provided by lab test and treatment group; subjects will be categorized according to the most severe postbaseline abnormality grade for a given lab test.

For all summaries of laboratory abnormalities, the denominator is the number of subjects with nonmissing postbaseline values up to 28 days after last dose date for the Overall Treatment Phase and up to Week 24 dose date for the Randomized Treatment Phase.

The maximum postbaseline grade observed up to 28 days after last dose date or the Week 24 dose date will be tabulated for each laboratory test, and percentages will be based on the number of subjects with a postbaseline evaluation of the specific laboratory test. The laboratory abnormalities during the Follow-up Phase will also be summarized.

A by-subject listing of graded laboratory abnormalities will be provided by subject number and visit in chronological order. This listing will include all test results that were collected throughout the study for the lab test of interest, with all applicable severity grades displayed.

### 7.2.2. ALT Elevation

#### 7.2.2.1. ALT Elevation without Declining Hepatic Function

All subjects with an ALT elevation on treatment, defined as  $ALT > 2 \times \text{Baseline}$  or on-treatment nadir and  $\geq 10 \times \text{ULN}$ , should have the ALT findings confirmed within 3 days of receipt of the original results.

#### 7.2.2.2. ALT Elevation with Declining Hepatic Function

Subjects with confirmed ALT elevation with evidence of declining hepatic function should be discontinued from study treatment. This is defined as:

- ALT elevation  $\geq 2 \times \text{Baseline}$  (Day 1) or nadir and  $> 2 \times \text{ULN}$  AND
  - Direct bilirubin increases to  $\geq 2 \times \text{Baseline}$  (Day 1) and  $\geq 2 \times \text{ULN}$  OR
  - Albumin decline from Baseline  $\geq 0.5 \text{ g/dL}$  OR international normalized ratio (INR)  $> 2 \times \text{Baseline}$  (Day 1) OR
  - Symptoms of liver inflammation (eg, fatigue, weakness, lack of appetite, nausea, vomiting, jaundice or discolored feces)

The number of subjects meeting the above criteria will be summarized by treatment group. Clinical signs or symptoms of liver inflammation will not be included in the summary. For individual laboratory tests, subjects will be counted once based on the most severe postbaseline values. For the composite criteria, subjects will be counted once when the criteria are met at the same visit. The denominator is the number of subjects in the Safety Analysis Set who have nonmissing postbaseline values. A listing of subjects who met at least 1 of the above criteria will be provided.

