10. History of malignancy other than HCC unless the subject's malignancy has been in complete remission off chemotherapy and without additional medical or surgical interventions during the 3 years before Screening

11. History or presence at Screening of electrocardiogram (ECG) abnormalities deemed clinically significant, in the opinion of the Investigator
12. History of hypersensitivity or idiosyncratic reaction to any components or excipients of the investigational drug
13. History of any significant food or drug-related allergic reactions such as, anaphylaxis or Stevens-Johnson syndrome
14. The following exclusionary laboratory results at Screening:
  - Hemoglobin <12g/dL for males or <11g/dL for females
  - Platelet count <100,000/mm^3
  - White blood cell count <2,500/mm^3
  - Absolute neutrophil count <1,500/mm^3
  - Albumin <lower limit of normal
  - History of thyroid disease poorly controlled on prescribed medications, with thyroid-stimulating hormone (TSH), free triiodothyronine or free thyroxine (T4) outside the normal limits
  - Total bilirubin >1.2 × ULN unless known Gilbert's syndrome; subjects with Gilbert's syndrome are eligible for study participation if the direct bilirubin is within the normal range
  - Direct bilirubin >1.2 × ULN
  - ALT ≤1 × ULN or ≥10 × ULN
  - Serum alpha fetoprotein (AFP) ≥100 ng/mL. If AFP at Screening is > ULN but <100 ng/mL, the subject is eligible if hepatic imaging prior to initiation of study drug reveals no lesions indicative of possible HCC
  - International Normalized Ratio (INR) >1.5 × ULN (unless on a stable anticoagulant regimen)
  - Glomerular filtration rate <60 mL/min/1.73 m^2 by Chronic Kidney Disease Epidemiology Collaboration equation ([Levey et al 2009](#))
  - Serum creatinine >1.5 × ULN
  - Any other laboratory abnormality deemed clinically significant by the Sponsor or the Investigator
15. Subjects receiving prohibited concomitant medications or medications that should be avoided (as outlined in [Section 6.6](#) and [Appendix 5](#)) within 7 days or 5 half-lives (if known), whichever is longer, prior to administration of the first dose of study drug (Day 1) and for the duration of the study period. Please refer to Exclusion Criterion #1 for criteria regarding liver protecting and/or ALT lowering agents

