## **9.4. Management of ALT Elevations**

All subjects participating in the study will be closely monitored for ALT elevations and/or signs of potential decline in hepatic function. Subjects experiencing ALT elevations  $\geq 2 \times$  Baseline or on-treatment nadir and  $> 2 \times$  ULN during study treatment or during post-treatment follow-up should be closely monitored with regular Unscheduled Visits every 1 to 2 weeks at the discretion of the Investigator. At these visits, the following laboratory tests will be performed: ALT, aspartate aminotransferase (AST), total bilirubin (if total bilirubin is elevated, reflex to direct bilirubin), serum albumin, INR and creatine kinase. The Investigator will determine if other Unscheduled Visit

assessments ([Section 7.8](#)) should be performed. Additionally, the following guidance is provided for management of subjects with ALT elevations:

- ALT elevation without declining hepatic function
  - All subjects with an ALT elevation on treatment, defined as ALT  $>2 \times$  Baseline or on-treatment nadir and  $\geq 10 \times$  ULN, should have the ALT findings confirmed within 3 days of receipt of the original results. All subjects should return for an Unscheduled Visit and complete all Unscheduled Visit procedures ([Section 7.8](#)).
  - If the ALT elevation is confirmed, then an additional Unscheduled Visit will be performed to further evaluate the subject. At this visit, the following tests will be performed: ALT, AST, total bilirubin (if total bilirubin is elevated, reflex to direct bilirubin), serum albumin, INR, creatine kinase, HBV DNA, quantitative HBV serologies (HBeAg [reflex qualitative HBeAg if quantitative HBeAg is less than the lower limit of quantification (LLOQ)] and HBsAg [reflex qualitative HBsAg if quantitative HBsAg is  $<$ LLOQ]), HAV IgM, HCV RNA, HDV RNA, and HEV IgM. The Investigator will determine if other assessments specified in [Section 7.8](#) should be performed.
    - If an intercurrent illness is determined to be causal, subjects with an ALT elevation without declining hepatic function and without contraindications may continue assigned treatment (ie, 731, ETV and Peg-IFN $\alpha$  as applicable) and the intercurrent illness should be treated as deemed medically appropriate by the Investigator.

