- ALT elevation with declining hepatic function
  - Subjects with confirmed ALT elevation with evidence of declining hepatic function should discontinue Peg-IFN $\alpha$  (if applicable) and 731 (if applicable). Entecavir may be continued at the discretion of the Investigator in accordance with local practice. Elevation of ALT with declining hepatic function is defined as:
    - ALT elevation  $\geq 2 \times \text{Baseline}$  or nadir and  $>2 \times \text{ULN}$  AND
      - Direct bilirubin increase to  $\geq 2 \times \text{Baseline}$  and  $\geq 2 \times \text{ULN}$  OR
      - Albumin decline  $\geq 0.5 \text{ g/dL}$  OR INR  $>2 \times \text{Baseline}$  OR
      - Symptoms of liver inflammation (eg, fatigue, weakness, lack of appetite, nausea, vomiting, jaundice, or discolored feces)
  - Subjects with evidence of declining hepatic function should return for an Unscheduled Visit ([Section 7.8](#)) every 2 to 5 days until the relevant laboratory values stabilize. Subjects whose hepatic function has stabilized should continue to be monitored weekly (or more frequently as deemed necessary by the Investigator) until the relevant laboratory values return to normal or Baseline.

All subjects with ALT elevation without or with declining hepatic function should continue to be followed on their regular study visit schedule, with the addition of Unscheduled Visits ([Section 7.8](#)) as described previously. If the ALT elevation has not substantially resolved by the last study follow-up visit, subjects should continue to return to clinic as deemed medically appropriate by the Investigator and in consultation with the Sponsor. The Unscheduled Visit module in the case report form should be utilized as needed to gather additional clinical and laboratory data until the ALT elevation is documented to be either resolved or resolving (defined as consistent ALT declines of 10% or more or normalization of ALT) on at least 2 successive visits.

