#### **7.2.1.1.      Treatment-Emergent Laboratory Abnormalities**

Treatment-emergent laboratory abnormalities are defined as values that increase at least 1 toxicity grade from Baseline at any postbaseline time point, up to and including the date of last dose of any study drug plus 28 days for the Overall Treatment Phase. For the Randomized Treatment Phase, the treatment-emergent laboratory abnormalities will be summarized up to the last dose at Week 24.

If the relevant baseline laboratory value is missing, any abnormality of at least Grade 1 observed within the time frame specified above will be considered treatment emergent.

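### SAP 7.2.2.2 counts a nadir-relative ALT criterion on the most severe value without defining nadir, and its by-group count names no treatment phase

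*Combined protocol and SAP*

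**What the plan says.** SAP 7.2.2.2 carries over the criterion of Protocol 9.4 for ALT elevation with declining hepatic function. ALT must be at least twice Baseline or nadir and above 2 × ULN, with at least one further finding (direct bilirubin, albumin, INR or symptoms). In its general monitoring rule Protocol 9.4 writes the reference as "Baseline or on-treatment nadir and", followed by the ULN threshold. SAP 7.2.2.1 also says on-treatment nadir; 7.2.2.2 says only nadir. No section of the SAP says how the nadir is derived.

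The counting rules in 7.2.2.2 are:

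- Individual tests: "For individual laboratory tests, subjects will be counted once based on the most severe postbaseline values".
- Composite: "For the composite criteria, subjects will be counted once when the criteria are met at the same visit".
- Denominator: "The denominator is the number of subjects in the Safety Analysis Set who have nonmissing postbaseline values".

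The count is by treatment group, with no phase and no end date. A listing of subjects who met at least one criterion is also planned.

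Neighbouring sections do name phases. SAP 7.2.1.1 says: "For the Randomized Treatment Phase, the treatment-emergent laboratory abnormalities will be summarized up to the last dose at Week 24". SAP 7.1.6 (adverse events) and 7.2.1.2 (laboratory denominators) make the same split. Under SAP 1.2 all three groups receive VBR+ETV from Week 24 to Week 48, then ETV alone to Week 60. Under SAP 3.2 a subject's actual treatment is taken to differ from the randomized one only if it differed throughout, so Group 3 stays under ETV+Peg-IFN.

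**The concern.** Direct bilirubin, albumin and INR are each compared with a fixed Baseline (bilirubin also with the ULN), so the worst value settles whether the subject qualifies. ALT against nadir is different: the same value may or may not qualify depending on what came before it. A rule that looks at one extreme value can therefore look at the wrong one.

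The population makes the pattern plausible. Protocol 5.3 excludes "ALT ≤1 × ULN or ≥10 × ULN", so subjects enter with ALT between 1 and 10 × ULN, and one randomization stratum is ALT of at least 5 × ULN. A subject who enters high, improves and then rebounds moderately is the case at issue.

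The missing phase matters because Group 2 against Group 3 up to Week 24 is the only randomized contrast that isolates VBR added to ETV+Peg-IFN. After Week 24 both groups receive VBR+ETV. Safety is the primary objective, and abnormal laboratory results are part of the primary endpoint. A count running over the whole study blurs that contrast and places events on VBR under a label without VBR.

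**Working it through.** The plan gives no expected count or rate for this table, so there is no figure to reproduce. The ALT courses below are illustrations in multiples of ULN; the thresholds come from SAP 7.2.2.2 and Protocol Appendix 3.

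**1. High baseline with a rebound.** Baseline 6.0, then 5.0, 0.8, 3.5.

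- Value by value: 3.5 ≥ 2 × 0.8 = 1.6, and 3.5 > 2. The criterion is met.
- Highest value only: the peak is 5.0. Twice Baseline is 2 × 6.0 = 12.0, and no lower value precedes the peak. Since 5.0 < 12.0, the criterion is not met and the subject is not counted.

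**2. Do the graded tables show it?** Appendix 3 puts ALT of 5.0 to <10.0 × ULN at Grade 3 and 2.5 to <5.0 × ULN at Grade 2.

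- Baseline 6.0 is Grade 3, the early 5.0 is Grade 3 and the rebound to 3.5 is Grade 2.
- SAP 7.2.1.1 requires a rise of one grade or more over Baseline. There is none, so nothing is treatment-emergent.
- The maximum postbaseline grade in 7.2.1.2 is 3, and it comes from the early 5.0 rather than the rebound.

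**3. Low baseline, for comparison.** Baseline 1.8, then 1.5, 0.8, 4.0. The peak is the rebound itself: 4.0 ≥ 2 × 0.8 = 1.6, and 4.0 > 2. Both methods count the subject. The gap is therefore limited to subjects whose early on-treatment ALT exceeds the later rebound.

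**4. Composite.** It is judged visit by visit, so the most-severe-value rule does not touch it. Its ALT limb still refers to a nadir with no derivation.

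**5. Phase.** Scheduled postbaseline chemistry visits (Protocol 7.5 to 7.7 and Appendix 1):

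| Period | Weeks | Visits | Group 3 treatment |
|---|---|---|---|
| Randomized | 2, 4, 8, 12, 16, 20, 24 | 7 | ETV+Peg-IFN |
| Weeks 24–48 | 28, 32, 36, 40, 44, 48 | 6 | VBR+ETV |
| Follow-up | 52, 56, 60 | 3 | ETV |

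As planned, (6 + 3)/16 = 9/16 = 56% of these visits fall after Week 24. SAP 1 and 2.2 record that the study was terminated in July 2022 and that subjects moved to ETV follow-up, so the actual share may be smaller. With 60/3 = 20 subjects per group, each Group 3 subject whose first event falls after Week 24 adds 1/20 = 5 percentage points to the ETV+Peg-IFN figure.

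**The case against.** **The rule can be read so that it works.** For a relative criterion, the most severe value could mean the one furthest above its reference. In step 1 that is 3.5/0.8 = 4.4 against 5.0/6.0 = 0.83, and the subject is counted. This stands as a possible reading. It makes the defect an ambiguity rather than a rule that must fail, but the SAP does not say it, and the highest value is the plainer reading.

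**General phase text may apply.** SAP 3.6.4 gives a Week 24 cut for the Randomized Treatment Phase, and 7.2.1.2 words its denominator rule broadly for laboratory abnormalities. A programmer might carry both into 7.2.2.2. That is fair, but 7.2.2.2 is a separate section that sets its own denominator and names no phase.

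**Pooling by original group is planned elsewhere.** The Overall Treatment Phase tables in 7.1.6 and 7.2.1 do it under the same grouping rule. This also stands: an overall count is not wrong in itself. What is missing here is the Week 24 count beside it.

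**The data remain visible.** The listings keep every value, and graded ALT abnormalities to Week 24 are already planned by group. The listings limit the harm but do not correct a by-group count, and step 2 shows that the graded tables miss this pattern.

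A reader might go further and infer that subjects whose ALT only falls would be counted as elevations. That requires comparing a value with a nadir reached later. Protocol 9.4 and SAP 7.2.2.1 use on-treatment nadir as the reference for a rise, so the documents do not support expecting that result. Nor is leaving symptoms out of the summary a hidden departure from Protocol 9.4; the SAP says so openly: "Clinical signs or symptoms of liver inflammation will not be included in the summary".

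**Conclusion.** The point holds as a gap in one table. On the plain reading of 7.2.2.2, the individual ALT count misses a rebound from nadir that stays below an early on-treatment value, and the graded tables do not recover it. The nadir is undefined for both the individual count and the composite. The by-group count names no phase, so as written it combines the randomized comparison with a period in which all groups receive VBR+ETV.

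A reader might want to turn the entry range into a proportion of rebounds missed, or into a diluted risk ratio. The documents give no ALT courses, rebound rates or event risks by phase, so no such figure can be supported. The example shows that the rule can miss a qualifying subject, not how often it will.

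The conclusion rests on reading the most severe ALT as the highest. For phase, it rests on 7.2.2.2 standing on its own text. Early termination reduces the data after Week 24 and so the size of the second problem. It should be corrected, but it affects neither the other safety tables nor the management of any subject.

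**What to change.** Change SAP 7.2.2.2 only; this is analysis and alters no clinical rule.

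1. For ALT, compare each postbaseline value with Baseline and with the lowest earlier on-treatment value. Count a subject once if any value meets the criterion. Use the same nadir in the composite, and state whether it carries into follow-up.
2. Keep the most-severe-value rule for direct bilirubin, albumin and INR.
3. Report the individual and composite counts for the Randomized Treatment Phase (to Week 24) separately from the period after Week 24 and from follow-up, each with its own denominator.

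The cost is wording and programming, with no new data. SAP 3.6.2 already defines the Randomized Treatment and Follow-up Phases. If the SAP is already final, SAP 1 provides for recording the change in the synoptic report. There are two drawbacks: counts per phase will be small in groups of about 20, and judging every value gives more weight to unscheduled draws in closely monitored subjects.

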### 7.3. Vital Signs

Descriptive statistics will be provided by treatment group for vital signs (systolic and diastolic blood pressure [mmHg], pulse [beats/min], respiration [breaths/min], and body temperature [°C]) as follows:

- Baseline value
- Values at each postbaseline visit
- Change from baseline at each postbaseline visit

A Baseline value will be defined as the last available value collected on or prior to the date/time of first dose of study drug. Change from Baseline to a postbaseline visit will be calculated for any postbaseline visit including follow-up visits.

In the case of multiple values in an analysis window, data will be selected for analysis as described in [Section 3.6.3](#).

A by-subject listing of vital signs will be provided by subject ID number and visit in chronological order.

### 7.4. Prior and Concomitant Medications

Medications collected at screening and during the study will be coded using the current version of the World Health Organization (WHO) Drug dictionary (WHODrug Global 1Sep2020).

#### 7.4.1. Prior Medications

Prior medications are defined as any medications taken before a subject took the first study drug.

Prior medications will be summarized by Anatomical Therapeutic Chemical (ATC) drug class Level 2 and preferred name using the number and percentage of subjects for each treatment group and overall. A subject reporting the same medication more than once will be counted only once within each ATC drug class. The summary will be ordered alphabetically by ATC medical class and then by preferred term in order of descending overall frequency within each ATC medical class. For drugs with the same frequency, sorting will be done alphabetically.

A medication will be considered as a prior medication if it meets one the following criteria:

- A medication with a start date prior to the first dose date of study drug will be included in the prior medication summary regardless of when the stop date is.
- If a partial start date is entered, the medication will be considered prior unless the month and year (if day is missing) or year (if day and month are missing) of the start date are after the first dose date.

- A medication with a completely missing start date will be included in the prior medication summary, unless otherwise specified.

Summaries will be based on the Safety Analysis Set.

#### 7.4.2. **Concomitant Medications**

Concomitant medications are defined as medications taken while a subject took study drug. Use of concomitant medications will be summarized by ATC drug class Level 2 and preferred name using the number and percentage of subjects for each treatment group. A subject reporting the same medication more than once within each ATC drug class will be counted only once when calculating the number and percentage of subjects who received that medication. Medications may appear under multiple ATC drug classes. The summary will be ordered alphabetically by ATC medical class and then by preferred term in descending overall frequency within each ATC medical class. For drugs with the same frequency, sorting will be done alphabetically.

A medication will be considered as a concomitant medication if it meets one the following criteria:

- A medication with a start date prior to or on the first dose date of study drug, and continued to be taken after the first dose date.
- A medication started after the first dose date but prior to or on the last dose date of study drug.
- If a partial start date is entered, any medication with the month and year (if day is missing) or year (if day and month are missing) before the study drug stop date, and with the stop date after the first dose date of study drug. If a partial stop date is entered, any medication with the month and year (if day is missing) or year (if day and month are missing) after the date of first study drug
- A medication started and stopped on the same day as the first dose date or the last dose date of study drug
- Medications with completely missing start and stop dates, unless otherwise specified.

A medication with a stop date prior to the date of first dose date of study drug or a start date after the last dose date of study drug will be excluded from the summary.

Summaries of prior and concomitant medications will be based on the Safety Analysis Set.

All the prior and concomitant medications will be provided in a by-subject listing sorted by subject ID number and administration date in chronological order.

## 7.5. **Electrocardiogram Results**

A shift table of the investigators' assessment of ECG results at each visit compared with baseline values will be presented by treatment group using the following categories:

- normal
- abnormal (not clinically significant)
- abnormal (clinically significant)
- missing/not done

The number and percentage of subjects in each cross-classification group of the shift table will be presented. Subjects with a missing value at Baseline or postbaseline will not be included in the denominator for percentage calculation.

A by-subject listing for ECG assessment results will be provided by subject ID number and visit in chronological order.

